1.3 STUDY RATIONALE AND BENEFIT–RISK ASSESSMENT

The results from the Phase I studies, nonclinical toxicology studies, and studies in a nonclinical model of SLE support further evaluation of GDC-0853 as a potential treatment for SLE. The goal of the parent Phase II study (GA30044) is to evaluate the safety and efficacy of GDC-0853 in combination with standard of care (SOC) in patients with moderate to severe SLE. The study tests two dose levels of GDC-0853 in comparison with placebo when added to background SOC. The study was powered to detect a meaningful clinical benefit in a composite measure of disease activity across multiple organ systems (see Section 3.3.4.1) and includes multiple safety assessments and monitoring by an unblinded Internal Monitoring Committee (IMC) and a Scientific Oversight Committee.

This OLE Study GA30066 will evaluate the long-term safety and efficacy of GDC-0853 in patients with SLE who have completed the ongoing, blinded Phase II Study GA30044. In this study, all patients will receive GDC-0853 starting at a dose of 200 mg twice a day (BID) for up to 48 weeks of treatment. Patients will be allowed to continue and adjust their background SOC therapy.

Inhibition of BTK offers a promising mechanism for the treatment of autoimmune diseases, such as RA and SLE (see the GDC-0853 Investigator's Brochure); however, data from clinical studies are lacking. Humans with a mutation in the XLA gene and who, therefore, lack functional BTK from birth, can live relatively normal lives on a standard therapy of IV Ig (Kaveri et al. 2011), suggesting that BTK can be safely inhibited, especially in people with established immune systems. GDC-0853 did not deplete IgG substantially during short-term treatment of healthy subjects in Phase I studies (see GDC-0853 Investigator's Brochure), but it is not known whether long-term treatment of patients will induce depletion. Therefore, IgG levels will be carefully monitored in this study. Clinical data to date suggest that IgG levels in patients with an established

immune system may not be significantly depleted, perhaps because BTK inhibitors target only the kinase domain and other BTK activities remain intact (Byrd et al. 2013).

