4.1.1 Inclusion Criteria

Patients must meet the following criteria for study entry:

- Signed Informed Consent Form (see Section 4.4.1)
- Age 18–76 years, inclusive, at time of signing Informed Consent Form
- Able to comply with the study protocol, in the investigator's judgment
- Completion of Study GA30044 up to 48 weeks
- Acceptable safety and tolerability during Study GA30044 as determined by the investigator
- Women of childbearing potential must have a negative urine pregnancy test at baseline

A serum pregnancy test is needed on Day 1 only if the urine pregnancy test is positive.

- For women of childbearing potential (including those who have had a tubal ligation): Agreement to remain abstinent (refrain from heterosexual intercourse) or use a contraceptive method with a failure rate of < 1% per year during the treatment period and for at least 60 days after the last dose of study drug.

A woman is considered to be of childbearing potential if she is postmenarcheal, has not reached a postmenopausal state (≥ 12 continuous months of amenorrhea with no identified cause other than menopause), and has not undergone surgical sterilization (removal of ovaries and/or uterus).

Examples of contraceptive methods with a failure rate of < 1% per year include bilateral tubal ligation, male sterilization, established proper use of hormonal contraceptives that inhibit ovulation, hormone-releasing intrauterine devices, and copper intrauterine devices. Women using estrogen-containing hormonal contraceptives as a method of contraception must also use a barrier, such as a male condom, in conjunction with the hormonal contraceptives.

The reliability of sexual abstinence should be evaluated in relation to the duration of the clinical trial and the preferred and usual lifestyle of the patient. Periodic abstinence (e.g., calendar, ovulation, symptothermal, or postovulation methods) and withdrawal are not acceptable methods of contraception.

- For men: agreement to remain abstinent (refrain from heterosexual intercourse) or use contraceptive measures, and agreement to refrain from donating sperm, as defined below (also see [Appendix 5](#))

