4.1.2 Exclusion Criteria

Patients who meet any of the following criteria will be excluded from study entry:

- Met protocol-defined treatment-stopping criteria during Study GA30044
- An adverse event in Study GA30044 that required permanent discontinuation of study drug
- During Study GA30044, treatment with any therapy that is prohibited in this study (see Section [4.3.2](#))
- In the opinion of the investigator, any new (since initially enrolling in the Phase II Study GA30044), significant, uncontrolled comorbidity or new clinical manifestation (related to SLE or not) that 1) requires medications not allowed in this protocol (see Section [4.3.2](#)) or 2) could put the patient at undue risk from a safety perspective

If the Principal Investigator has questions related to exclusion, he or she should consult the Medical Monitor.

- Pregnant or breastfeeding, or intending to become pregnant during the study or within 60 days after the last dose of study drug
- Any uncontrolled or clinically significant laboratory abnormality that would affect safety, interpretation of study data, or the patient's participation in the study in the opinion of the investigator in consultation with the Medical Monitor
- Any major episode of infection requiring hospitalization or treatment with IV antibiotics within the last 4 weeks of Study GA30044
- Evidence of active, latent, or inadequately treated infection with *Mycobacterium tuberculosis* (TB) as defined as follows:
 - A positive QuantiFERON[®]-TB Gold (QFT) or T-SPOT[®] TB test or a Mantoux purified protein derivative (PPD) skin test (performed per Centers for Disease

Control and Prevention [CDC] guidelines using 5 tuberculin units per 0.1 mL) result of ≥ 5 mm of induration, performed at the Week 44 visit of Study GA30044 or later, prior to entry into Study GA30066

- Patients with a history of bacillus Calmette-Guérin vaccination should be screened using the QFT test only.
- A positive QFT test should be considered a positive diagnostic TB test.
- If initial QFT is indeterminate, perform a confirmatory test with either QFT or T-SPOT. The Principal Investigator may consult with the Medical Monitor to discuss selection of confirmatory test based on the patient's disease status and baseline immunosuppression.
- An indeterminate QFT test followed by a negative QFT or negative T-SPOT test should be considered a negative diagnostic TB test.

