- An indeterminate QFT test followed by an indeterminate QFT test or borderline or positive T-SPOT test should be considered a positive diagnostic TB test.
- Patients who experienced a de novo or reactivated serious viral infection, such as hepatitis B virus or hepatitis C virus (HCV) during Study GA30044
 - Positive hepatitis B surface antigen (HBsAg) or hepatitis C serology (regardless of treatment status) or positive hepatitis B core antibody (HBcAb) (tested at Week 44 of Study GA30044 or later, prior to entry into Study GA30066) are exclusionary.
- Patients who developed a malignancy (with the exception of non-serious local and resectable basal or squamous cell carcinoma of the skin) during the Phase II Study GA30044
- 12-lead ECG at the Week 48 visit of Study GA30044 that demonstrates clinically relevant abnormalities that may affect patient safety or interpretation of study results, including the following:
 - QTcF > 440 msec demonstrated by at least two ECGs > 30 minutes apart
- Current treatment with medications that are well known to prolong the QT interval at doses that have a clinically meaningful effect on QT, as determined by the investigator
 - The investigator may contact the Sponsor for confirmation if needed. The investigator may reference the CredibleMeds[®] Web site:
<https://www.crediblemeds.org/pdftemp/pdf/CompositeList.pdf>.
- Estimated glomerular-filtration rate (based on the 4-variable Modification of Diet in Renal Disease equation) < 30 mL/min or on chronic renal replacement therapy
- Laboratory values from the Week 44 visit of Study GA30044 (which may be repeated once at a later unscheduled visit, if necessary) that meet the following criteria:
 - AST or ALT $> 1.5 \times$ ULN (unless due to known autoimmune hepatitis)
 - Total bilirubin > 1.2 ULN

- Amylase or lipase $> 2 \times \text{ULN}$
- Hemoglobin $< 7 \text{ g/dL}$
- ANC $< 1.5 \times 10^9/\text{L}$
- Absolute lymphocyte count (ALC) $< 0.5 \times 10^9/\text{L}$
- Platelet count $< 50,000/\mu\text{L}$

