6.4 SAFETY ANALYSES

The analyses will include all patients who received at least one dose of the study drug during this OLE study. Safety will be analyzed based on reported/documented adverse events including AESIs, and changes in laboratory results, ECGs, physical findings, and vital signs.

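### Section 6.4 safety rates pool former-placebo patients with former-active patients who completed and tolerated GA30044; for events linked to earlier intolerance they are expected to understate the rate among all GDC-0853 starters

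*Combined protocol and SAP*

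**What the plan says.** Section 6.4 defines the safety set in one sentence: "The analyses will include all patients who received at least one dose of the study drug during this OLE study". It goes on to list adverse events, laboratory results, ECGs, physical findings and vital signs. A summary by parent treatment cohort is planned in Section 6.5, for efficacy only.

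Section 4.1.1 makes entry conditional on "Completion of Study GA30044 up to 48 weeks" and on "Acceptable safety and tolerability during Study GA30044 as determined by the investigator". Section 4.1.2 excludes a patient for "An adverse event in Study GA30044 that required permanent discontinuation of study drug" and a patient who "Met protocol-defined treatment-stopping criteria during Study GA30044". It also excludes patients who had a serious viral infection or a malignancy (with a skin-cancer exception) during the parent study. Further exclusions are Week 44 liver, pancreatic-enzyme, haemoglobin, neutrophil, lymphocyte or platelet results outside set limits.

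On the parent design, Section 1.3 states: "The study tests two dose levels of GDC-0853 in comparison with placebo when added to background SOC". Section 3.3.1 says that 200 mg BID is the higher of these doses, and Section 4.2.2.1 gives it to everyone in the extension. The primary objective (Section 2, Table 1) is long-term safety over a treatment period of up to 48 weeks.

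**The concern.** For a patient from an active arm, entry depends on outcomes of the drug itself. Infection, cytopenia, hepatotoxicity and malignancy are named potential risks in Section 1.3.2, and each also appears among the entry exclusions. Patients who had such problems during the first 48 weeks are more likely to be missing from the Section 6.4 set, and their events lie outside it.

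A former-placebo patient has not been selected on tolerance of GDC-0853 and contributes the first 48 weeks on drug. Without a split by parent arm, one pooled rate mixes early exposure in that group with later exposure in a selected group. That rate, or a low rate among former-active patients, could be read as risk staying acceptable or declining with longer treatment when only the mix of patients has changed. Long-term safety is the primary objective, so this reading matters.

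**Working it through.** **Plan figures.** There is nothing to reproduce. Section 6.1 gives about 240 as a ceiling without a sample-size calculation. The documents give no event rates, no parent discontinuation rate and no parent allocation ratio.

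**What Section 6.4 observes, by parent arm.**

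| Parent arm | Prior GDC-0853 at OLE Day 1 | Selected on tolerating | Person-time observed |
|---|---|---|---|
| Placebo | none | placebo plus background therapy | weeks 0 to 48 on drug |
| Lower dose | 48 weeks | the lower dose | weeks 48 to 96 on drug, after a dose change |
| 200 mg BID | 48 weeks | 200 mg BID | weeks 48 to 96 on drug |

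**Illustration 1 (all inputs assumed).** A share s of starters is susceptible, with yearly risk r of an event that bars entry; the rest have risk b. Individual risks do not change, and one year stands in for each 48-week period.

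- Year 1 incidence: y1 = s·r + (1−s)·b
- Susceptible share among entrants: s' = s(1−r) / [s(1−r) + (1−s)(1−b)]
- Year 2 incidence among entrants: y2 = s'·r + (1−s')·b

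Worked case, s = 10%, r = 60%, b = 2%:

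- y1 = 0.10×0.60 + 0.90×0.02 = 0.078
- s' = 0.04/(0.04 + 0.882) = 0.0434
- y2 = 0.0434×0.60 + 0.9566×0.02 = 0.0452
- ratio y2/y1 = 0.579, a fall of 42%

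Corners of the assumed range, b = 2%:

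| s | r | y1 | y2 | Fall |
|---|---|---|---|---|
| 5% | 30% | 3.4% | 3.0% | 11% |
| 5% | 60% | 4.9% | 3.2% | 34% |
| 20% | 30% | 7.6% | 6.2% | 18% |
| 20% | 60% | 13.6% | 7.4% | 46% |

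The range is therefore 11% to 46%. With b = 5% the same grid gives 5% to 36%.

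**Illustration 2 (all inputs assumed).** Here the event counted need not be the one that bars entry. Susceptible patients have RR times the event rate of the others. A fraction q1 of susceptible patients and q0 of the others is removed before entry.

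- sO = s(1−q1) / [s(1−q1) + (1−s)(1−q0)]
- Ratio of the extension rate to the all-starter rate = [(1−sO) + sO·RR] / [(1−s) + s·RR]

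For s = 20%, RR = 3, q1 = 50%, q0 = 10%: sO = 0.10/(0.10 + 0.72) = 0.122, and the ratio is 1.244/1.400 = 0.89. Over s = 10% to 30%, RR = 2 to 5 and q1 = 30% to 80%, with q0 = 10%, the ratio runs from 0.98 to 0.61. It is 1.00 when RR = 1 or q1 = q0. It exceeds 1 only if susceptible patients are removed less often than others, the reverse of what the entry rules aim at.

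**What counting from first dose would add.** In the worked case, first events in year 2 make up 0.04×0.60 + 0.882×0.02 = 0.0416 of all starters. Two-year cumulative incidence is 0.078 + 0.0416 = 0.120. The extension-only display shows 4.5% among entrants. The year 2 figure among entrants stays 4.5% under either analysis; only the cumulative figure brings in the 7.8%.

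**The case against.** The strongest reply is that everyone dosed in the extension is the correct full safety set for this study. The objective concerns a further treatment period in patients who finished GA30044, and for them the entry rules introduce no bias. That stands. A reader might infer that the Section 6.4 set is wrong or its rates simply biased; the documents do not support that without naming all GDC-0853 starters as the reference, a population Section 6.4 does not claim to describe.

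The size is also uncertain. Illustration 1 assumes that the counted event always bars entry, which most adverse events do not. Infection requiring hospitalization or IV antibiotics, for example, excludes only if it fell in the last 4 weeks of GA30044. Selection may be weaker for the lower-dose arm, which was selected on tolerating that dose. A reader might take 42% or 46% as an estimate for this trial; it is not one.

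A reader might also infer that the excluded patients' events are lost, or that counting from first dose removes the selection. Neither follows. Those events belong to GA30044, which has its own safety evaluation. After Week 48, interval rates in former-active patients come from the same entrants under any time origin.

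Finally, Section 3.1.1 lets the monitoring committees see unblinded parent data, and Section 6.7 allows data cuts for submission with the main studies. Neither defines an integrated analysis, and the data analysis plan mentioned in Section 6.5 is cited for efficacy. An integrated summary may be intended at programme level, but these documents do not state one.

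**Conclusion.** The point holds as a limit on interpretation and a gap in the planned displays. Section 6.4 pools first-period exposure in former-placebo patients with second-period exposure in former-active patients selected for completing and tolerating GA30044, and states no limitation.

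For events linked to earlier intolerance, the former-active rate is expected to lie below the all-starter rate. The direction rests on one assumption: that the entry rules remove susceptible patients more often than others, which is what they are written to do. The magnitude rests wholly on assumed inputs: a fall of 11% to 46% in the first illustration, 0.98 to 0.61 times the all-starter rate in the second, and no effect for events unrelated to susceptibility. A split by parent arm would separate the two kinds of exposure but would not undo selection within the active arms. The entry rules themselves are not in question. This should be addressed, at low cost, by additions to the analysis.

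**What to change.** Keep the Section 6.4 analysis, present it by parent arm (placebo, lower dose, 200 mg BID), and state that it applies to patients who completed and tolerated GA30044.

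Add to Section 6.4:

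- **A supportive analysis from first GDC-0853 dose in either study.** Include every GA30044 patient dosed with GDC-0853, whether or not they entered the extension, and former-placebo patients from OLE Day 1. Give cumulative incidence and exposure-adjusted rates by time since first dose. Split by parent dose, because the lower-dose arm changes dose at OLE entry and time since first dose is otherwise confounded with that change.
- **A non-entry table.** For each parent arm, give the number of GA30044 patients who did not enter and the reasons.
- **A note on interpretation.** Interval rates after Week 48 in former-active patients come only from OLE entrants and must not be read as risk falling with exposure.

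No patients, visits or procedures are added, and the sponsor holds both datasets. The cost is extra tables after the parent study is unblinded. Cumulative rates may look less favourable; post-Week 48 rates will not change.

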6.5 EFFICACY ANALYSES

Patient efficacy data will be summarized separated by treatment cohort during the blinded study (GA30044), in addition to overall summaries. Efficacy summary will be based on the intent-to-treat population, defined as all eligible patients enrolled into this OLE study. Analyses of additional study populations (e.g., completers and per protocol [excluding major protocol violators]) will be performed as supportive evaluations. Additional subgroup analyses may be conducted on an exploratory basis. Details will be provided in the data analysis plan.

6.6 PHARMACOKINETIC ANALYSES

The PK analyses will include patients with sufficient data to enable estimation of key parameters (e.g., area under the concentration–time curve, predose concentrations, and half-life).

Systemic GDC-0853 exposure will be evaluated using a population PK approach, and estimates of PK parameters will be generated. The extent of inter-patient variability will be evaluated, and potential sources of variability will be assessed. Relationships between exposure, efficacy, and safety endpoints will be explored and additional PK analyses will be conducted during and/or at the end of the study as appropriate.

6.7 INTERIM ANALYSIS

No formal interim analysis is planned. Data cuts may be performed at appropriate time points for inclusion in the submission with the main studies to support the safety profile.

7. DATA COLLECTION AND MANAGEMENT

7.1 DATA QUALITY ASSURANCE

The Sponsor will be responsible for data management of this study, including quality checking of the data. Data entered manually will be collected via EDC through use of eCRFs. Sites will be responsible for data entry into the EDC system. In the event of discrepant data, the Sponsor and its designee will request data clarification from the sites, which the sites will resolve electronically in the EDC system.

The Sponsor or functional service provider will produce an EDC Study Specification document that describes the quality checking to be performed on the data. Central laboratory data and any other electronic data will be sent directly to the Sponsor, using the Sponsor's standard procedures to handle and process the electronic transfer of these data.

eCRFs and correction documentation will be maintained in the EDC system's audit trail. System backups for data stored by the Sponsor and records retention for the study data will be consistent with the Sponsor's standard procedures.

PRO data will be collected on paper questionnaires. The data from the questionnaires will be entered into the EDC system by site staff.

7.2 ELECTRONIC CASE REPORT FORMS

eCRFs are to be completed through use of a Sponsor-designated EDC system. Sites will receive training and have access to a manual for appropriate eCRF completion. eCRFs will be submitted electronically to the Sponsor and should be handled in accordance with instructions from the Sponsor.

All eCRFs should be completed by designated, trained site staff. eCRFs should be reviewed and electronically signed and dated by the investigator or a designee.

At the end of the study, the investigator will receive patient data for his or her site in a readable format on a compact disc that must be kept with the study records. Acknowledgement of receipt of the compact disc is required.

7.3 SOURCE DATA DOCUMENTATION

Study monitors will perform ongoing source data verification and review to confirm that critical protocol data (i.e., source data) entered into the eCRFs by authorized site personnel are accurate, complete, and verifiable from source documents.

Source documents (paper or electronic) are those in which patient data are recorded and documented for the first time. They include, but are not limited to, hospital records, clinical and office charts, laboratory notes, memoranda, PROs, evaluation checklists, pharmacy dispensing records, recorded data from automated instruments, copies of transcriptions that are certified after verification as being accurate and complete, microfiche, photographic negatives, microfilm or magnetic media, X-rays, patient files, and records kept at pharmacies, laboratories, and medico-technical departments involved in a clinical trial.

Before study initiation, the types of source documents that are to be generated will be clearly defined in the Trial Monitoring Plan. This includes any protocol data to be entered directly into the eCRFs (i.e., no prior written or electronic record of the data) and considered source data.

Source documents that are required to verify the validity and completeness of data entered into the eCRFs must not be obliterated or destroyed and must be retained per the policy for retention of records described in Section 7.5.

To facilitate source data verification, the investigators and institutions must provide the Sponsor direct access to applicable source documents and reports for trial-related monitoring, Sponsor audits, and IRB/EC review. The study site must also allow inspection by applicable health authorities.

7.4 USE OF COMPUTERIZED SYSTEMS

When clinical observations are entered directly into a study site's computerized medical record system (i.e., in lieu of original hardcopy records), the electronic record can serve

as the source document if the system has been validated in accordance with health authority requirements pertaining to computerized systems used in clinical research. An acceptable computerized data collection system allows preservation of the original entry of data. If original data are modified, the system should maintain a viewable audit trail that shows the original data as well as the reason for the change, name of the person making the change, and date of the change.

